2.2. Secondary outcomes and endpoints

To determine the rate of voice and swallowing problems, patients will receive videofluoroscopic swallowing studies and voice evaluations pre-operatively and post-operatively (at Day 12, Week 6, Month 6, and 1 Year visits) to examine how voice and swallow function are affected by inclusion of a CND. Voice and/or swallow evaluations may be eliminated once necessary endpoints have been satisfied or the evaluation is no longer informative.¹

- Phonation Threshold Pressure (cm H₂O)
- Dysphonia Severity Index (DSI; +5 to -5)
- GRBAS (grade roughness breathiness asthenia strain)
- CAPE-V (0-100 on visual analog scale for voice quality parameters)
- Stroboscopy assessment (ratings 1 [most severe] to 4 [normal]) for vocal fold vibratory and movement parameters
- Glottal Function Index score
- Penetration-Aspiration Scale (0-8 score) from videofluoroscopic swallow study¹

To determine the degree to which quality of life (QOL) is compromised, qualitative analyses of patient interview data and validated surveys of general health quality, as well as QOL surveys specific to cancer, thyroid disease, voice and swallowing will be used to assess the impact of complications on patient's lives.

- SF-12 MCS and PCS scores
- EORTC QLQ C30 scale scores
- ThyCA-QOL score
- EAT-10 dysphagia inventory score
- VHI score (collected by UW ENT department during the participant's voice evaluation, and by study personnel if no voice evaluation is needed)
- Themes, codes from interview transcripts (using qualitative research methods)

¹ With the elimination of swallow studies for patients enrolled after 12/01/2016 collection of data for this endpoint ceased.

To determine whether accurate quality of life measures can be extracted from patient interview narratives, patient interview data will be converted into usable datasets using natural language processing techniques and is then compared to QoL surveys specific to cancer and thyroid disease.

- Interview transcripts
- SF-12 MCS and PCS scores
- EORTC QLQ30 scale scores
- ThyCA-QoL score

To determine clinical recurrence rates, measures of thyroglobulin levels (a reliable surrogate marker for future recurrence), and clinical evidence of recurrent disease (using either I-131 imaging or neck ultrasound), will be made at Month 6 and 1 Year visits.

- Percent of patients with a 1 Year recombinant thyroid-stimulating hormone (rTSH) stimulated Thyroglobulin level <1 ng/ml

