- Unstimulated Thyroglobulin just prior to beginning the Week 6 radioactive iodine treatment
- Stimulated Thyroglobulin at the time of Week 6 radioactive iodine treatment (if RAI is given)
- Unstimulated Thyroglobulin at Month 6 >1 ng/mL
- Stimulated Thyroglobulin at 1 Year >2 ng/mL
- Biopsy-proven disease identified on neck ultrasound or I-131 uptake at either Month 6 or 1 Year post surgery, and reevaluated annually while enrolled in the study

For those patients who do experience thyroid cancer recurrence, this typically does not manifest until 10 to 20 years after their initial treatment. For this reason, in order to capture true clinical recurrence rates, participants who receive a diagnosis of PTC, as confirmed by final surgical pathology, and continue to receive care within the University of Wisconsin Hospital system will be followed through chart review in Health Link as well as University of Wisconsin's endocrine surgery outcomes database until their cancer recurs or they are lost to follow up.

Radioactive iodine treatment, ultrasound, and thyroglobulin monitoring are all part of the standard treatment and follow up of thyroid cancer for nodules >1cm. The only test that will be done for research purposes is to check the thyroglobulin level prior to radioactive iodine, so that we can assess the completeness of surgical excision prior to administering radioactive iodine.

3. Study design

This study will compare total thyroidectomy which is the standard of care treatment for PTC at the University of Wisconsin with total thyroidectomy with prophylactic CND to also remove the lymph nodes near the thyroid. Both surgical procedures are widely practiced in the United States for the treatment of thyroid cancer and it is not known which procedure is best.

Participant Identification and Eligibility:

Participants will be primarily identified from all of our University of Wisconsin endocrine surgery and otolaryngology clinics.

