Patients randomized to Arm 2 will be receive total thyroidectomy with an ipsilateral CND. The CND will be performed as described by a consensus conference of the ATA. This will include removal of the prelaryngeal nodes, the pretracheal nodes, and the paratracheal lymph nodes. The paratracheal dissection will be bounded superiorly by the cricoid cartilage and inferiorly by the innominate artery on the right and on the left by the axial plane where the innominate crosses the trachea. The superior parathyroid gland will be preserved in situ along with its primary blood supply from the superior branch of the inferior thyroid artery. The inferior parathyroid gland will be reflected laterally along with its blood supply from the inferior thyroid artery. Parathyroid autotransplantation will be performed if the glands are devascularized during dissection. Paratracheal tissue specimens will be examined for parathyroid glands that may be salvaged and transplanted before being removed from the sterile field. Suspected parathyroid glands will be confirmed by frozen section biopsy prior to autotransplantation.

Blinding: Both surgical procedures are performed through the same incision and post-operative care is identical. As such, the neck dressings are identical, allowing both the patients and study staff to be masked with regard to treatment arm randomization. Participants will remain blinded to treatment arm until the Day 12 follow-up appointment, at which point their pathology report will be reviewed with them, and unblinding will occur. Because subjective symptoms and calcium intake are two of our secondary endpoints, we will minimize participant and researcher bias in the description and treatment of post-operative symptoms in the immediate post-operative period. Because the risks of the two procedures and the post-operative instructions are identical for both arms, there is no risk associated with blinding the patients until their Day 12 follow-up. Participants who screen fail intra-operatively will be notified as to which procedure(s) was conducted immediately following surgery. The surgeon performing the procedure cannot and will not be blinded to the participant's treatment arm at any time.

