It is difficult to coordinate voice and swallow evaluations with regularly scheduled patient visits. If the study team is unable to schedule these procedures on the same day, the subject is given the option of returning on a different day of his or her choosing or waiving the evaluation(s) in question at that time point. If an exam is missed, the exam will be scheduled at the subject's next time point. To adequately address the secondary endpoints of the study, the study staff only needs to know if the vocal cord is working and, if it is not working, if it recovers; this can be assessed with only one post-operative time point. Ideally, the study team also hopes to understand the time course of recovery after surgery; therefore, we aim to evaluate patients at each time point. The research-only voice and swallow evaluations do not affect clinical care for thyroid cancer patients.

Subjects will receive an unstimulated thyroglobulin test approximately 6 weeks after surgery. Thyroglobulin reaches its nadir 3-4 weeks post-operatively in most patients, making the Week 6 time point ideal for collection. In multivariate analysis, the postoperative thyroglobulin level is often found to be an independent predictor of persistent or recurrent disease with a level above 0.2 ng/mL considered "elevated". Based on this result as well as the pathology report, the subject's treating endocrinologist will determine his or her risk status. According to the 2015 American Thyroid Association Management Guidelines for Adult Patients with Thyroid Nodules and Differentiated Thyroid Cancer, RAI remnant ablation is not routinely recommended after thyroidectomy in low-risk patients, although consideration of specific features of the individual patient that could modulate recurrence risk, disease follow-up implications, and patient preference are relevant to decision making regarding RAI. We will not require low-risk patients to undergo RAI remnant ablation in accordance with these guidelines; instead, their low risk status and thyroglobulin level < 0.2 ng/mL will classify their response to therapy as excellent. Should low-risk patients choose to undergo RAI remnant ablation, they will follow the protocol outlined below.

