In all intermediate- and high-risk subjects and low-risk subjects who choose to undergo RAI remnant ablation therapy, radioactive iodine will be administered at 4-20 weeks post-operatively and will be administered with rTSH. For consistency all subjects will be treated with 50 mCi of radioactive iodine unless it is strongly recommended otherwise based on specific features of the individual patient. Microscopic nodal involvement found on pathologic review will not influence the treatment dose of radioactive iodine, but the presence or absence of micrometastatic versus macrometastatic disease will be tracked for future analyses. Thyroglobulin levels will be checked after the rTSH stimulation in order to assess the burden of disease prior to radioactive iodine treatment. Following radioactive iodine administration, levothyroxine will be administered to maintain TSH < 0.5 uIU/mL. Labs will be checked at 6-8 week intervals until TSH level is in the goal range and stable.

At Month 6 and 1 Year visits, TSH, unstimulated thyroglobulin and anti-thyroglobulin antibody will be measured. Additionally, all patients will receive a neck ultrasound at these time points to further evaluate for recurrence.

If the subject underwent RAI remnant ablation, recombinant TSH will be administered and a blood sample testing for the stimulated thyroglobulin level will be obtained at the 1 Year visit. If the stimulated thyroglobulin is greater than 2 ng/mL and the neck ultrasound is negative, a whole body scan will be obtained. Elevated thyroglobulin and/or positive whole body scanning will prompt further evaluation with ultrasound, CT, MRI, or CT-PET as needed. All participants will be followed for a minimum of 1 year after treatment. Long term follow-up tracking the incidence of disease recurrence will be conducted throughout the entirety of the study, with the goal of tracking patients beyond the active study phase through our prospective endocrine surgical database.

Long-term follow-up: Participants who receive a diagnosis of PTC, as confirmed by final surgical pathology, and continue to receive care within the University of Wisconsin Hospital system will be followed through chart review and the endocrine surgery outcomes database until their cancers recur or they are lost to follow up. Clinical documentation of cancer recurrence only, if it occurs, will be abstracted from their electronic medical records.

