Post-operative care in hospital: After surgery, participants will remain in the hospital overnight per surgeon preference and laboratory evaluations will be performed per standard of care.

Post-operative Day 1: The participant will be educated on the signs and symptoms of hypocalcemia and be given detailed instruction on how to treat these symptoms per standard of care. They will be given a study log to fill out which will allow them to record the frequency and severity of symptoms and the number of doses of calcium taken. This will be completed and returned to study staff at the Day 12 visit.

Day 12 visit: Physical and laboratory evaluations will be performed per standard of care. A comprehensive voice and swallow⁵ evaluation will be conducted; this will be considered a research procedure unless the participant is experiencing difficulty swallowing or there is evidence of vocal fold dysfunction. The participant will also complete a QOL survey and participate in a qualitative interview per study protocol.

Week 6 visit: 48 hours prior to the Week 6 visit day, participants will have a blood sample drawn to establish post-operative thyroglobulin levels and assess response to treatment. During the visit, participants will complete QoL surveys and participate in a qualitative interview. If the patient's voice or swallow function was impaired at the Day 12 visit, additional voice and swallow⁵ evaluations will also be performed.

At this time the treating endocrinologist will assess the subject's risk profile based on the criteria outlined in section 3 of the protocol. If the patient is classified as intermediate- or high-risk or if the patient is classified as low-risk but chooses to undergo RAI remnant ablation, he or she will be treated according to the following standard schedule:

- Day 1: rTSH injection
- Day 2: rTSH injection
- Day 3: 50 mCu I-131 therapy administered²
- Day 5: Stimulated thyroglobulin lab
- Day 5-17: Whole Body Scan performed

Month 6 visit: Physical and laboratory evaluations, as well as an ultrasound of the neck, will be performed per standard of care. PTH and calcium samples required for the study will be drawn at this time. A QOL survey and qualitative interview will be completed. If the patients' voice or swallow function was impaired at the Week 6 visit, additional voice and swallow⁵ evaluations will also be performed.

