1 Year visit: Patients will receive a neck ultrasound and labs per standard of care. If a patient underwent RAI remnant ablation, a stimulated thyroglobulin level after rTSH administration will be obtained to assess response to therapy. A QOL survey and qualitative interview will be completed. If the patients' voice or swallow⁵ function was impaired at the Month 6 visit, additional voice and swallow evaluations will also be performed.

Follow-up: Patients will receive a quality improvement follow-up survey between 1 and 6 weeks after the completion of their last study activity. Patients who meet criteria for long term follow-up will continue to be followed through chart review and the endocrine surgery outcomes database.

Time required for study procedures: 120 minutes for voice and swallow evaluation^{3,5}
15-30 minutes for QOL survey
60-90 minutes for qualitative interview

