12.7. Participant cost and payment

Cost

Participants are not expected to incur additional costs from participation as clinical care costs that are not considered standard of care will be covered for all participants.

Payment

Participants will be provided \$20 in reimbursement for each completed study visit (participants completing the study will have 5 visits).

Clinical care costs that are not considered standard of care will be covered for all participants including 6 month calcium and PTH testing. For consistency all pre-operative ultrasounds for lymph node staging will be performed by a dedicated radiologist at the University of Wisconsin and this expense will be covered by the trial.

For our primary recurrence endpoint we would like to have all patients undergo recombinant TSH stimulated thyroglobulin testing.

13. Funding sources

This study is being funded by an R01 Grant.

14. Publication policy

This study will be registered with ClinicalTrials.gov.

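### Two 1-Year stimulated thyroglobulin endpoints are listed without restriction but measured only after radioactive iodine, so comparing arms on them compares subsets formed after randomisation

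*Combined protocol and SAP*

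**What the plan says.** **Endpoints.** The recurrence list in section 2.2 includes "Percent of patients with a 1 Year recombinant thyroid-stimulating hormone (rTSH) stimulated Thyroglobulin level <1 ng/ml" and "Stimulated Thyroglobulin at 1 Year >2 ng/mL". Neither carries an RAI condition. The Week 6 stimulated Tg item in the same list does carry one, in parentheses.

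**Collection.** Section 3 (post-operative follow-up) says "If the subject underwent RAI remnant ablation, recombinant TSH will be administered", with the stimulated sample taken at the 1 Year visit. Section 7 (1 Year visit) says "If a patient underwent RAI remnant ablation, a stimulated thyroglobulin level after rTSH administration will be obtained". Section 12.7 says "For our primary recurrence endpoint we would like to have all patients undergo recombinant TSH stimulated thyroglobulin testing". Section 8.1 also mentions a primary recurrence endpoint at 1 year without defining it. The schedule of activities codes 1-Year stimulated Tg as standard of care, as needed, with no RAI footnote.

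**Who receives RAI.** Section 3 gives it to intermediate- and high-risk patients and to low-risk patients who want it. The treating endocrinologist sets the risk class after the Week 6 unstimulated Tg: "Based on this result as well as the pathology report". Section 7 (Week 6 visit) repeats the element of choice: "if the patient is classified as low-risk but chooses to undergo RAI remnant ablation".

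**Timing.** Randomisation takes place in the operating room (section 5.4). Section 3 adds: "Participants will remain blinded to treatment arm until the Day 12 follow-up appointment".

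**Analysis.** The Summary commits to comparing recurrence between cohorts. Section 8.2 describes an analysis for the primary aims only and gives no denominator or missing-data rule for the recurrence endpoints.

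**The concern.** An endpoint worded as a percentage of patients needs a denominator. If it is everyone randomised, the plan does not collect the data. If it is those tested, the denominator is set by a treatment decision made weeks after randomisation.

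The documents supply two reasons for caution about that subset. First, entry to it can depend on arm. The pathology report feeds the risk class, and only the CND arm has a routine central-node specimen. Section 3 keeps microscopic nodes from changing the RAI dose, but says nothing of the kind about the decision to give RAI. Section 2.2 also describes the pre-RAI Tg as a check on completeness of excision, which is something the randomised operation may change. Second, entry is tied to outcome: section 3 calls postoperative Tg a predictor of persistent or recurrent disease.

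At stake is the early recurrence read-out that would be set against the complication results. Both listed 1-Year Tg endpoints are stimulated; the only unstimulated Tg endpoint that section 2.2 lists after Week 6 is at Month 6.

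**Working it through.** **1. The plan's own figures.** The documents give no sample size, power, RAI uptake or expected rate for stimulated Tg. The one sample size, 116 (58 per arm, section 8.1), is for Day 1 transient hypoparathyroidism at 12% versus 36%. A two-sided 0.05 test with 80% power and continuity correction gives 57 per arm, 114 in total, so that figure reproduces closely. It does not bear on this endpoint.

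**2. Order of events.** Randomisation (day of surgery), then pathology review and unblinding (Day 12), then unstimulated Tg and risk class (Week 6), then RAI (4-20 weeks), then stimulated Tg at 1 year if RAI was given. Membership of the tested group is settled after randomisation.

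**3. What selection alone could do.** Assume CND has no true effect on Tg.
- b: share given RAI in both arms for reasons unrelated to the node specimen (assumed 0.30).
- 0.60: microscopic central-node involvement, from section 1.1. That figure is for central nodes generally; the trial's CND is ipsilateral.
- g: share of node-positive patients not already due RAI who are moved to it by the node finding (assumed 0.25, 0.5 or 1).
- qb, qa: proportion with Tg <1 ng/ml among base and added RAI patients (assumed).

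Added share in the CND arm: a = (1 - b) × 0.60 × g. Tested rate: CND = (b·qb + a·qa)/(b + a); no CND = qb. Gap = CND minus no CND.

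For b = 0.30, a = 0.105, 0.21 and 0.42, so 40.5%, 51% and 72% of the CND arm are tested against 30%.

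| qb, qa | g = 0.25 | g = 0.5 | g = 1 |
|---|---|---|---|
| 0.75, 0.65 | -2.6 | -4.1 | -5.8 |
| 0.70, 0.90 | +5.2 | +8.2 | +11.7 |
| qa = qb | 0 | 0 | 0 |

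Example: (0.30 × 0.70 + 0.42 × 0.90)/0.72 = 0.588/0.72 = 81.7%, against 70.0%.

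The g = 1 column is the extreme, in which every such node-positive patient is moved to RAI. With g = 1 and the same pairs of rates, the gap runs from -8.4 to +16.9 points at b = 0.10 and from -2.0 to +4.1 at b = 0.70. These are illustrations, not bounds.

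**4. Precision without any bias.** Half-width = 1.96 × √[0.8 × 0.2 × (1/n1 + 1/n2)], with 80% success and 30% RAI in both arms assumed. The arm sizes are the ends of the 70-140 range in section 8.1.
- 35 per arm: all tested, ±18.7 points; 30% tested, ±33.4 (11 per arm) or ±34.2 (10.5 per arm, unrounded).
- 70 per arm: all tested, ±13.3; 30% tested (21 per arm), ±24.2.

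If RAI use differed as in the g = 1 case (72% versus 30%; 25.2 and 10.5 tested at 35 per arm), the half-width would be about ±29.

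**The case against.** Several points on the other side have force.

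- **Low-risk patients are not left unclassified.** Section 3 counts low risk with Tg below 0.2 ng/mL as an excellent response. This stands as a second response route, but it rests on the Week 6 level and is not tied to the 1-Year endpoints.
- **Recurrence does not rest on stimulated Tg alone.** Section 2.2 also lists Month 6 unstimulated Tg and biopsy-proven disease at Month 6 or 1 Year, and it relies on long-term chart review for true recurrence rates. This stands and limits the point to the stimulated Tg endpoints.
- **Bias needs a link that the documents do not state.** A reader might infer that node findings push more CND patients into RAI and so tilt the comparison in a known direction. No passage says that microscopic nodes change the risk class, and a footnote in section 7.1, written about dose, expects no significant nodal involvement. That stronger reading is not supported.
- **No passage prescribes an unadjusted comparison among tested patients.** True, but none prescribes anything else. Section 8.2 names RAI dose as an example factor, for primary aims only, which does not address who is tested.
- **Table 7.1 may already carry the restriction.** Its stimulated Tg entries bear a footnote mark whose text appears lost; a fragment about remnant ablation at Week 6 surfaces in section 7.4. The table should not be counted as a conflict.
- **The alternatives share the as-needed code in the schedule.** True, but section 3 states that unstimulated Tg will be measured and that every patient will have the ultrasound at Month 6 and 1 Year.

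**Conclusion.** The inconsistency is clear: 1-Year stimulated Tg is an unrestricted endpoint in section 2.2, is collected only after RAI in sections 3 and 7, and is wished for in all patients in section 12.7. Followed as written, an arm comparison would use post-randomisation subsets and only part of each arm. Confidence in that is high.

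Confidence that bias is present, or how large it is, is low. Its sign and size cannot be derived from the documents. On the assumptions shown, it ranges from zero, through about -3 to +5 points with modest selection, to -6 to +12 in the extreme case at 30% base RAI use. The loss of precision needs no bias, only partial RAI use.

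The point should be fixed but is not critical. Section 2.2 places recurrence among the secondary outcomes, and the sample size for the Day 1 endpoint is unaffected. A reader might conclude that the whole recurrence aim fails; it does not, because other listed measures are not conditional on RAI.

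**What to change.** - Make the early recurrence comparison between the two randomised arms, analysed as randomised, on measures that section 3 schedules whether or not RAI was given. Two are already section 2.2 endpoints: biopsy-proven disease found at the scheduled Month 6 and 1 Year ultrasounds, and Month 6 unstimulated Tg above 1 ng/mL.
- Add a pre-specified summary of 1-Year unstimulated Tg with anti-Tg antibody (a cut-off or continuous), and say openly that it is a new endpoint using data already collected.
- Report 1-Year stimulated Tg descriptively in RAI-treated patients, with denominators and RAI use by arm. Do the same for disease found through I-131 scanning or through work-up triggered by Tg or a scan, flagged by how it was found.
- Reconcile the schedule of activities and sections 2.2, 3, 7 and 12.7 on who has the 1-Year stimulated test, and confirm the Table 7.1 footnote. Which patients should be tested is for the investigators to settle.
- Leave the long-term follow-up unchanged.

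The cost is endpoint and analysis wording, including one added endpoint, with no new tests. The main downside is that the as-randomised comparison estimates the effect of surgery plus any RAI that follows it, not of CND alone. Triggered work-up may also still vary with RAI use, which is why the route of detection has to be recorded.

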6.1. Participant identification

We will recruit patients from the University of Wisconsin Endocrine Surgery and Otolaryngology Clinics. We will also promote the study to endocrinologists throughout the state, specifically targeting endocrinologists in areas with a greater proportion of underrepresented minorities than found in the Madison area. We have well established referral patterns from Winnebago County, IL, which has a significantly higher proportion of underrepresented minority patients than Dane County where our institution is based.

We will work closely with referring endocrinologists to perform the needed long-term follow up for the participants in the study. We will try to condense all study visits to 4 time points, which are already established for routine clinical follow up. Because participation in the study will require additional time at these appointments we will provide a small monetary reimbursement for participation in each of the study visits (\$20). The cost of all study procedures that are not the standard of care will be covered as part of participation in the clinical trial.

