Based on our experience with qualitative research and the rates of objective complications in the patients enrolled to date, we've determined that we need to enroll at least 62 patients in order to obtain an adequate dataset to examine the impact of hypocalcemia and 70 patients in order to obtain an adequate dataset to examine the impact of vocal cord dysfunction. While we will continue to recruit as many patients as feasible, based on these calculations, if we are able to enroll at least 70 patients, this should give us the data necessary to evaluate all of our study aims.

Therefore, we will plan to randomize 70 - 140 patients. We will plan to recruit patients up until year 5 of the study as the primary recurrence endpoint will be at 1 year. Given the fact that we anticipate having at least 89 eligible patients per year, we should meet our recruitment goal while allowing for at least 1 year of follow up in all study patients.

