12.5. Patient confidentiality

Information about study participants will be kept confidential and managed according to the requirements of the Health Insurance Portability and Accountability Act of 1996 (HIPAA). Those regulations require a signed subject authorization informing the participant of the following:

- what protected health information (PHI) will be collected from participants in this study
- who will have access to that information and why
- who will use or disclose that information
- the rights of a research participant to revoke their authorization for use of their PHI

All participants will be assigned a study-specific ID number. We will maintain a master list linking each participant's medical record number (MRN) with a study-specific ID number. This list is to be maintained in a location separate from any study data. Only study staff listed on the IRB application shall have access to the list.

All information obtained and associated data files will be confidential and will be kept in a locked file or password protected computer. The risk of breach of confidentiality regarding participation in the study outside of the scope of the research will be handled by carefully controlling access to study data only to personnel on the research team.

Confidentiality will be protected further by: (1) using a participant log form that contains only the minimum necessary protected health information (PHI) concerning participants, and storing this log in a locked area when not in use, (2) not sharing PHI with any outside institution, (3) coding data collection forms with a consecutive participant number that is not derived from any participant personal identifiers, and linking that data collection form to the participant log, and (4) storing the participant log and data collection forms separately.

All study data will be kept for 10 years after publication of study findings. All data will be destroyed by deletion from computer files and/or shredding.

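### Long-term follow-up records recurrences but no time at risk, so it does not secure an unbiased long-term recurrence rate by arm

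*Combined protocol and SAP*

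**What the plan says.** Comparing recurrence between the cohorts is one of the aims listed in the Summary, and Section 2.2 places it among the secondary outcomes. Section 2.2 says of recurrence that "this typically does not manifest until 10 to 20 years after their initial treatment", and gives this as the reason for long-term follow-up, which is done "in order to capture true clinical recurrence rates".

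The long-term follow-up paragraph of Section 3 sets the rules. Participants with pathology-confirmed papillary cancer who "continue to receive care within the University of Wisconsin Hospital system will be followed through chart review and the endocrine surgery outcomes database" are tracked until recurrence or loss to follow-up. On the data item: "Clinical documentation of cancer recurrence only, if it occurs, will be abstracted from their electronic medical records".

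Three other places bear on this:
- Section 6.1 (Participant identification): "We will work closely with referring endocrinologists to perform the needed long-term follow up for the participants in the study". It describes no route by which those practices' findings reach the trial.
- Section 8.1 (Sample size determination) justifies the recruitment period "as the primary recurrence endpoint will be at 1 year".
- Section 8.2 (Analysis of endpoints) lists evaluation times that end at 1 Year. It contains no time-to-event method and no censoring rule.

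**The concern.** A recurrence rate needs events and the time over which each patient could have been seen to have one. The plan secures the first and is silent on the second. If only recurrences are abstracted, the absence of an entry has several possible meanings: disease-free under surveillance, moved to another provider, or dead. These contribute very different amounts of information over 10 to 20 years.

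Two consequences follow. Dividing documented recurrences by all randomised patients understates the rate in each arm. And if patients leave UW care at different rates in the two arms, the comparison is distorted as well. Differential departure is conceivable: patients learn their allocation at the Day 12 visit, and the trial's hypothesis is that central neck dissection (CND) causes more complications, which could change how long a patient stays with the centre. That last step is my inference; the documents do not state it.

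Section 9.3 hopes the results will support future guidelines, so an understated long-term rate, or a 1-year rate read as a long-term one, could mislead.

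**Working it through.** **Inputs from the documents.** Recurrence window 10 to 20 years (Section 2.2). Long-term follow-up restricted to UW care, recurrence the only item abstracted (Section 3). Minimum follow-up 1 year (Section 3). Randomisation target 70 to 140, so 35 to 70 per arm; original requirement 58 per arm (Section 8.1). No recurrence rate, retention rate or recurrence sample size is given.

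**The plan's own figure.** The only sample size is 116, for transient hypoparathyroidism at 12% versus 36%, alpha 0.05, power 0.8. The two-sided formula is n = [1.96·√(2·0.24·0.76) + 0.842·√(0.12·0.88 + 0.36·0.64)]² / 0.24² = 48.5. With continuity correction, (48.5/4)·[1 + √(1 + 4/(48.5·0.24))]² = 56.5, so 57 per arm and 114 in total. That is within 2 of the stated 116. The figure stands, but it says nothing about recurrence.

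**Does any other section supply time at risk?**
- Section 3 ends follow-up at recurrence or loss. That implies an end date, but no field records it.
- Section 2.2 has yearly re-evaluation during enrolment, while Section 10.4 gives the duration of participation as 1 year after treatment.
- Section 6.1 involves outside endocrinologists but plans no data return.
- Section 8.2 plans nothing after 1 Year.
- Sections 2.2 and 3 name the endocrine surgery outcomes database. Its fields are not described, so it may or may not hold contact dates.

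**Size of the understatement.** Let R be the true long-term proportion recurring in an arm and c the share of recurrences that happen while the patient is still in UW care. Documented recurrences over all randomised patients estimate R·c, which is at most R; the shortfall is R·(1 − c). Using only patients still at UW as the denominator does not help, because without departure dates that group is not defined at each time.

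**Illustration of the mechanism (all rates assumed; not evidence about this trial).** Take R = 10% in both arms, recurrences spread evenly over years 10 to 20, and a fraction a leaving UW care each year independently of recurrence. Then c is the average of (1 − a)^t for t from 10 to 20.

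| a per year | c | Crude rate, R·c | Kaplan-Meier at 20 years, with dates |
|---|---|---|---|
| 2% | 74% | 7.4% | 9.96% |
| 5% | 47% | 4.7% | 10.05% |
| 10% | 22% | about 2.1% | 9.82% |

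The last column comes from 200,000 simulated patients censored at last contact. It shows that the missing dates are what is needed to recover the rate, provided departure is unrelated to recurrence.

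**Comparison between arms.** If c is equal in both arms it cancels from the ratio. If it differs, say 80% versus 60% (assumed), a true 10% in both appears as 0.10·0.80 = 8% versus 0.10·0.60 = 6%, a ratio of 0.75. At 58 per arm that is 4.6 versus 3.5 patients.

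**Power with full capture.** Two-sided normal approximation at alpha 0.05, recurrence rates assumed:

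| Per arm | 20% vs 10% | 10% vs 5% |
|---|---|---|
| 35 | 21% | 12% |
| 58 | 32% | 17% |
| 70 | 38% | 20% |

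**The case against.** The strongest reply is that the restriction to recurrence governs only what is taken from the electronic record. A second source, the outcomes database, is named, and tracking until loss implies that loss is identified somehow. Arm is known for every randomised patient, and disease status is assessed on schedule at Month 6 and 1 Year, with thyroglobulin described in Section 2.2 as a dependable surrogate for later recurrence. Section 3 calls tracking beyond the active phase a goal, and it feeds no planned test. The primary outcome is hypocalcemia, and power for recurrence is poor whatever is collected.

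Much of this stands. A reader might infer that the trial cannot produce any recurrence rate by arm. The documents do not support that: recurrences can be counted by arm, a 1-year rate by arm is available, and a censored estimate is possible if contact dates are taken from the chart or database. What does not stand is that the database already answers the point, since no section says it holds those dates or that they will be used.

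A reader might also infer from "All study data will be kept for 10 years after publication of study findings" that the data will be destroyed inside the recurrence window. That depends on which publication starts the clock and on whether the outcomes database counts as study data; neither is stated, so I do not rely on it.

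**Conclusion.** The concern holds in this form: the long-term follow-up, as described, does not secure an unbiased long-term recurrence rate by arm, although that is its stated purpose. A count over all randomised patients is a lower bound in each arm. The direction is clear from the text; the amount is not, because it depends on retention and recurrence rates the documents do not give. A bias between arms is possible but not shown. At these sample sizes a modest spurious difference would amount to about one patient (4.6 versus 3.5 in the example), so the main damage is to the rate itself.

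Severity is moderate. Recurrence is secondary, the powered endpoint is untouched, and the 1-year comparison can be made as planned. The conclusion assumes that the abstraction rule in Section 3 is followed literally and that the database is not already supplying last-contact dates to the trial.

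**What to change.** **Section 3, long-term follow-up (and the matching text in Section 2.2).** At each chart review or outcomes-database extract for a randomised patient, record:
- recurrence status and date;
- date of the last disease-free evaluation;
- date and reason for leaving UW care, or date of death.

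If the database already holds these items, say so and name it as the source.

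**Section 8.2.** Add a descriptive time-to-recurrence analysis by randomised arm, censored at the last disease-free evaluation, with loss to follow-up and deaths reported by arm. Describe the 1-year result as early disease status, not as the long-term recurrence rate.

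**Cost.** A few extra abstraction fields and some protocol wording; no new visits, tests or patients. The comparison remains low in power, so it should be reported as estimates with intervals. Censoring supplies the time at risk but does not cure departure that is itself related to recurrence, which is why loss should be shown by arm.

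Requesting records from outside practices would reduce loss further, but I do not recommend it on what is available. Section 12.5 rules out sharing protected health information with outside institutions, and the consent text is not in the documents. Both would have to be confirmed to allow it first.
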